16.3 Appendix 4 – Schedule of Events / Procedure

Cohort 1 and 2 Visit Schedule - Pregnant women enrolled between 13 0/7 - 27 6/7 gestational weeks

	PRENATAL						DELIVERY	POSTNATAL				
	Screening + V1	V2	V3	V4 ^b	V5 ^b	V6 ^c	V7	V8 ^e	V9 ^f	V10	V11	V12
Study timeline	D0	D14	D28-42	D56-84	D84-112	D112 - 140	Delivery	Delivery up to 7 days (where possible)	Delivery +14 days (where possible)	Delivery +28-42 days OR 70-84 days	Delivery +182 days (+/- 14 days)	Delivery +364 days (+/- 14 days)
Study window	D0	Day 10-21 post V1 (phone)	Day 28-42 post V1	Day 56-84 post V1	Day 28-42 post V3	Day 56-84 post second COVID vaccine	N/A	0 - 7 days post delivery	Day 12-16 post delivery (phone)	Day 28-42 OR 70-84 post delivery	Day 168-196 post delivery (phone)	Day 349-379 post delivery
Informed consent	X											
Screening bloods - maternal (HIV, Hep B, Syphilis) from routine prenatal visits	X (routine)											
Ultrasound dating and anomaly scan from routine prenatal visit	X (routine)											
Medical History	X											
Physical examination - maternal	X		(X)	(X)	(X)	(X)	(X)			(X)		
Vital signs, height and weight	X		X	X								
Vaccination	X		X ^a	X ^a								
COVID-19 immunogenicity bloods - maternal	X		X	X	X	X	X			X		X
eDiary review		X	X	X	X	X						
SAE/AES/Medically attended AE check		X	X	X	X	X		X	X	X	X	X
Concomitant medication check	X	X	X	X	X	X		X	X	X	X	X
Physical examination - infant							X					X
COVID-19 immunogenicity bloods - infant										X ^d		
Neurodevelopmental assessment (Ages & Stages questionnaire) - infant												X
Cord blood sample (selected sites)							X					
Colostrum / Breast milk sample (selected sites)								X	X			

^a For cohort 1, this will be a COVID-19 vaccine or pertussis-containing vaccine depending on randomisation to long or short course. A pertussis-containing vaccine may also be offered in cohort 2, 3, 4.
^b Participants will either have blood sampling for Neutralising Antibody, ELISpot, Intracellular Cytokine Staining assays at V4 or V5 depending on whether they are on the short course or long course.
^c This visit will take place if the window starts before their due date.
^d Infant is randomised at V9 to blood sampling at 4-6 weeks or 10-12 weeks after birth except cohort 3 (cohort 3 will have infant and maternal blood samples taken at 28-42 days post-delivery).
^e V8 only for breast milk sub-study sites or Cohort 3
^f V9 is a telephone call review except for breast milk sub-study sites (in brackets) - as required

Cohort 3 Visit Schedule - Pregnant women enrolled between 28 0/7 - 34 0/7 gestational weeks

	PRENATAL						DELIVERY	POSTNATAL				
	Screening + V1	V2	V3	V4	V5	V6	V7	V8 ^b	V9 ^c	V10	V11	V12
Study timeline	D0	D14	D28-42	No visit in this cohort	No visit in this cohort	No visit in this cohort	Delivery	Delivery up to 7 days (where possible)	Delivery +14 days (where possible)	Delivery +28-42 days	Delivery +182 days (+/- 14 days)	Delivery +364 days (+/- 14 days)
Study window	D0	Day 10-21 post V1 (phone)	Day 28-42 post V1				N/A	0 - 7 days post delivery	Day 12-16 post delivery (phone)	Day 28-42 post delivery	Day 168-196 post delivery (phone)	Day 349-379 post delivery
Informed consent	X											
Screening bloods - maternal (HIV, Hep B, Syphilis) from routine prenatal visits	X (routine)											
Ultrasound dating and anomaly scan from routine prenatal visit	X (routine)											
Medical History	X											
Physical examination - maternal	X		(X)				(X)	(X)		(X)		
Vital signs, height and weight	X							X				
Vaccination	X							X				
COVID-19 immunogenicity bloods - maternal	X		X				X			X		X
eDiary review		X	X						X	X		
SAE/AES/Medically attended AE check		X	X					X	X	X	X	X
Concomitant medication check	X	X	X					X	X	X	X	X
Physical examination - infant							X					X
COVID-19 immunogenicity bloods - infant										X ^a		
Neurodevelopmental assessment (Ages & Stages questionnaire) - infant												X
Cord blood sample (selected sites)							X					
Colostrum / Breast milk sample (selected sites)								X				

^a Cohort 3 will have infant and maternal blood samples taken at 28-42 days post-delivery

^b V8 only for breast milk sub-study sites or Cohort 3

^c V9 is a telephone call review except for breast milk sub-study sites (in brackets) - as required

Cohort 4 Visit Schedule - Pregnant women enrolled between 13 0/7 - 27 6/7 gestational weeks and received a COVID-19 vaccine before pregnancy or during first trimester (0 0/7 - 12 6/7 gestational weeks)

	PRENATAL					DELIVERY	POSTNATAL					
	Screening ^a	V1	V2	V3	V4 + V5	V6 ^b	V7	V8 ^c	V9 ^d	V10	V11	V12
Study timeline	Screening	D0	D14	D28-42	No visit in this cohort	D112 - 140	Delivery	Delivery to 7 days (where possible)	Delivery +14 days (where possible)	Delivery +28-42 days OR 70-84 days	D182 (+/- 14 days)	D364 (+/- 14 days)
Study window		<26 weeks gestation OR >26 weeks gestation	Day 10-21 post V1 (phone)	Day 28-42 post V1		Day 112 - 140 post V1	N/A	0 - 7 days post delivery (phone)	Day 12-16 post delivery (phone)	Day 28-42 OR 70-84 post delivery	Day 168-196 post delivery (phone)	Day 349-379 post delivery
Informed consent	X											
Screening bloods - maternal (HIV, Hep B, Syphilis) from routine prenatal visits	X (routine)											
Ultrasound dating and anomaly scan from routine prenatal visit	X (routine)											
Medical History	X											
Physical examination - maternal	X	(X)		(X)		(X)	(X)			(X)		
Vital signs, height and weight	X	X										
Vaccination	X	X										
COVID-19 immunogenicity bloods - maternal		X		X		X	X			X		X
eDiary review			X	X		X						
SAE/AESI/Medically attended AE check		X	X	X		X		X	X	X	X	X
Concomitant medication check	X	X	X	X		X		X	X	X	X	X
Physical examination - infant							X					X
COVID-19 immunogenicity bloods - infant										X ^e		
Neurodevelopmental assessment (Ages & Stages questionnaire) - infant												X
Cord blood sample (selected sites)							X					
Colostrum / Breast milk sample (selected sites)								X	X			

^a Screening and V1 can be done at the same time if randomisation to vaccination schedule allows.

^b V6 will take place if the window starts before their due date.

^c V8 only for breast milk sub-study sites or Cohort 3

^d V9 is a telephone call review except for breast milk sub-study sites

^e Infant is randomised at V9 to blood sampling at 4-6 weeks or 10-12 weeks after birth except cohort 3 (cohort 3 will have infant and maternal blood samples taken at 28-42 days post-delivery).

(in brackets) - as required

Cohort 1 and 2 Laboratory Sampling Schedule - Pregnant women enrolled between 13 0/7 - 27 6/7 gestational weeks

	PRENATAL						DELIVERY			POSTNATAL			
	Screening + V1	V2	V3	V4 ^b	V5 ^b	V6 ^c	V7	V8	V9	V10 ^d	V11	V12	
Study timeline	D0	D14	D28-42	D56-84	D84-112	D112 - 140	Delivery	Delivery up to 7 days	Delivery +14 days	Delivery + 28-42 days OR 70-84 days	D182 (+/- 14 days)	D364 (+/- 14 days)	
Study window	D0	Day 10-21 post V1	Day 28-42 post V1	Day 56-84 post V1	Day 28-42 post V3	Day 56-84 post second COVID vaccine	N/A	0 - 7 days post delivery	Day 12-16 post delivery	Day 28-42 OR 70-84 post delivery	Day 168-196 post delivery	Day 349-379 post delivery	
Vaccination	X	X ^e	X ^e	X ^e	X	X	X			X			
COVID-19 immunogenicity bloods - maternal	X Nexelis Anti-spike IgG	X Nexelis Anti-spike IgG	X Nexelis Anti-spike IgG	X Nexelis Anti-spike IgG	X Nexelis Anti-spike IgG	X Nexelis Anti-spike IgG	X Nexelis Anti-spike IgG			X Nexelis Anti-spike IgG		X Nexelis Anti-spike IgG	
	PHE Anti-nucleocapsid IgG ADCC	PHE Neutralising Abs ADCC	PHE Neutralising Abs ADCC	PHE Neutralising Abs ADCC	PHE Neutralising Abs ADCC	PHE Anti-nucleocapsid IgG Neutralising Abs ADCC	PHE Anti-nucleocapsid IgG Neutralising Abs ADCC					PHE Anti-nucleocapsid IgG ADCC	
	IMMUNOTEC ELISpot & ICS (7 sites)	IMMUNOTEC ELISpot & ICS (7 sites)	IMMUNOTEC ELISpot & ICS (7 sites)	IMMUNOTEC ELISpot & ICS (7 sites)	IMMUNOTEC ELISpot & ICS (7 sites)	SGUL Lab ELISpot & ICS (2 sites)	SGUL Lab ELISpot & ICS (2 sites)					IMMUNOTEC ELISpot & ICS (7 sites)	
Cord blood sample (at selected sites)						X Nexelis Anti-spike IgG	X Nexelis Anti-spike IgG						
Colostrum / Breast milk sample (at selected sites)							X SGUL Lab Anti-spike IgG ELISpot + ICS (2 sites)	X SGUL Lab Anti-spike IgG ELISpot + ICS (2 sites)	X SGUL Lab Anti-spike IgG ELISpot + ICS (2 sites)				
COVID-19 immunogenicity bloods - infant										X Nexelis Anti-spike IgG			
	Maternal: Up to 50mls (20mls red, 30mls green/ LIHep)	Maternal: Up to 50mls (20mls red, 30mls green/ LIHep)	Maternal: Up to 50mls (20mls red, 30mls green/ LIHep)	Maternal: Up to 50mls (20mls red, 30mls green/ LIHep)	Maternal: Up to 50mls (20mls red, 30mls green/ LIHep)	Maternal: Up to 50mls (20mls red, 30mls green/ LIHep)	Maternal: Up to 50mls (20mls red, 30mls green/ LIHep)	Maternal: Up to 50mls (20mls red, 30mls green/ LIHep)	Breast milk: 2-5mls	Maternal: Up to 20mls (20mls red) Infant: up to 5mls		Maternal: Up to 50mls (20mls red, 30mls green/ LIHep)	

^aThis will either be a COVID vaccine or pertussis-containing vaccine for cohort 1 depending on randomisation to long or short course. A pertussis-containing vaccine may also be offered in cohort 2, 3, 4.

^bParticipants will either have Neutralising Abs, ELISpot, intracellular Cytokine Staining assays at V4 or V5 depending on whether they are in the short course or long course.

^cThis visit will take place if the window starts before their due date.

^dInfant is randomised at V9 to blood sampling at 4-6 weeks or 10-12 weeks after birth except cohort 3. Cohort 3 will have infant and maternal blood samples taken at 28-42 days post-delivery.

Cohort 3 Laboratory Sampling Schedule - Pregnant women enrolled between 28 0/7 - 34 6/7 gestational weeks

	PRENATAL					DELIVERY		POSTNATAL				
	V1	V2	V3	V4	V5	V6	V7	V8	V9	V10**	V11	V12
Study timeline	Screening + V1	D14	D28	No visit in this cohort	No visit in this cohort	No visit in this cohort	Delivery	Delivery up to 7 days	Delivery +14 day	Delivery + 28-42 days	D182 (+/- 14 days)	D364 (+/- 14 days)
Study window	D0	Day 10-21 post V1	Day 28 post V1				N/A	0 - 7 days post-delivery	Day 12-16 post-delivery	Day 28-42 post-delivery	Day 168-196 post-delivery	Day 349-379 post-delivery
Vaccination	X							X				
COVID-19 immunogenicity bloods - maternal	X Nexelis Anti-spike IgG PHE ADCC		X Nexelis Anti-spike IgG PHE Neutralising Abs ADCC				X Nexelis Anti-spike IgG PHE Anti-nucleocapsid IgG Neutralising Abs ADCC			X Nexelis Anti-spike IgG		X Nexelis Anti-spike IgG PHE ADCC
Cord blood sample (at selected sites)	IMMUNOTEC ELISpot & ICS (7 sites)		IMMUNOTEC ELISpot & ICS (7 sites)				SGUL Lab ELISpot & ICS (2 sites)					IMMUNOTEC ELISpot & ICS (7 sites)
Colostrum / Breast milk sample (at selected sites)							X Nexelis Anti-spike IgG PHE Anti-nucleocapsid IgG SGUL Lab ELISpot & ICS			X SGUL Lab Anti-spike IgG ELISpot + ICS		
COVID-19 immunogenicity bloods - infant										X Nexelis Anti-spike IgG PHE Anti-nucleocapsid IgG		
Sample volumes (+ blood bottles)	Maternal: Up to 50mls (20mls red, 30mls green/ Lihsep)		Maternal: Up to 20mls (20mls red)				Maternal: Up to 50mls (20mls red, 30mls green/ Lihsep) Cord blood: up to 30mls	Colostrum: 1-2mls	Breast milk: 2-5mls	Maternal: Up to 20mls (20mls red) Infant: up to 5mls		Maternal: Up to 50mls (20mls red, 30mls green/ Lihsep)

** infant plus maternal blood samples to be taken at 28-42 days post-delivery

Cohort 4 Prenatal Laboratory Sampling Schedule - Pregnant women enrolled between 13 0/7 - 27 6/7 gestational weeks and received a COVID-19 vaccine before pregnancy or during first trimester (0 0/7 - 12 6/7 gestational weeks)

	PRENATAL							DELIVERY				POSTNATAL			
	Screening	V1	V2	V3	V4	V5	V6	V7	V8	V9	V10**	V11	V12		
Study timeline	Screening	D0	Day 14	D28-42	No visit in this cohort	No visit in this cohort	D112 - 140	Delivery	Delivery up to 7 days	Delivery +14 days	Delivery + 28-42 days OR 70-84 days	D182 (+/- 14 days)	D364 (+/- 14 days)		
Study window	<26 weeks gestation OR >26 weeks gestation	Day 10-21 post V1	Day 28-42 post V1	Day 28-42 post V1	Day 112 - 140 post V1	N/A	0 - 7 days post delivery	Day 12-16 post delivery	Day 28-42 OR 70-84 post delivery	Day 168-196 post delivery	Day 349-379 post delivery				
Vaccination	X														
COVID-19 immunogenicity bloods - maternal	X Nexelis Anti-spike IgG PHE Anti-nucleocapsid IgG ADCC IMMUNOTEC ELISpot & ICS (7 sites)			X Nexelis Anti-spike IgG PHE Neutralising Abs ADCC IMMUNOTEC ELISpot & ICS (7 sites)		X Nexelis Anti-spike IgG	X Nexelis Anti-spike IgG PHE Anti-nucleocapsid IgG Neutralising Abs ADCC SGUL Lab ELISpot & ICS (2 sites)			X Nexelis Anti-spike IgG			X Nexelis Anti-spike IgG PHE Anti-nucleocapsid IgG ADCC IMMUNOTEC ELISpot & ICS (7 sites)		
Cord blood sample (at selected sites)															
Colostrum / Breast milk sample (at selected sites)									X SGUL Lab Anti-spike IgG ELISpot + ICS	X SGUL Lab Anti-spike IgG ELISpot + ICS					
COVID-19 immunogenicity bloods - infant										X Nexelis Anti-spike IgG PHE Anti-nucleocapsid IgG					
Sample volumes		Maternal: Up to 50mls (20mls red, 30mls green/ LHep)		Maternal: Up to 20mls (20mls red)			Maternal: Up to 50mls (20mls red, 30mls green/ LHep) Cord blood: up to 30mls		Breast milk: 2-5mls	Maternal: Up to 20mls (20mls red) Infant: up to 5mls			Maternal: Up to 50mls (20mls red, 30mls green/ LHep)		

** Infant is randomised at v9 to blood sampling at 4-6 weeks or 10-12 weeks after birth.

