7 TRIAL PROCEDURES

Screening + study visit 1 (Maternal)

This visit will take place between 13 0/7 – 27 6/7 gestational weeks (for the earlier gestational weeks group) or between 28 0/7 – 34 0/7 gestational weeks (for the later gestational weeks group) at the participating institution. Eligibility will be confirmed, the study will be discussed in more detail and women will be asked to sign a consent form. They will then be asked about demographic details (including NHS number), past medical history, receipt of any prior dose of a COVID-19 vaccine, details of the current pregnancy including the results of antenatal screening and scans to ensure that they are eligible for the study. The participant's antenatal medical notes will be reviewed. Details will be collected about concomitant medication. A physical examination will be performed, and vital signs, height and weight will be recorded. Immunogenicity blood samples will be obtained.

Cohort 1, 2, 3: Participants will be randomised to a single group to receive one type of COVID-19 vaccine with the first dose to be given at visit 1.

Cohort 4: Participants will receive the same vaccine as given pre-pregnancy or during their first trimester (0 0/7 – 12 6/7 gestational weeks) and randomised to either receiving the booster dose before or after 26 weeks' gestation.

Vaccination will be given by members of the study team who are trained and experienced in vaccine administration and in emergency procedures in the event of an allergic reaction. They will have access to emergency medication and equipment. The vaccinations will be given according to the advice in the “Green Book” and the Summary of Product Characteristics (SmPC). An eDiary will be set up for the participant and they will be given instructions to complete the diary regularly for 28 days following vaccination. The participant will be observed for a period of 20 minutes following vaccination to assess for allergic adverse events.

Study visit 2 (Maternal) all cohorts

14 days (10 days – 21 days) after first vaccination review by telephone call.

- SAE / AESI / MAAE check
- Concomitant medication check
- eDiary review

Study visit 3 (Maternal) all cohorts

Day 28-42 following the first vaccination at the participating institution.

- SAE / AESI / MAAE check
- Concomitant medication check
- eDiary review
- Targeted physical examination if indicated
- Immunogenicity blood samples will be collected
- **Cohort 1.**
 - Vital signs pre-vaccination

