 - **Vaccination with COVID-19 vaccine if randomised to the short interval boost or dTaP/IPV if randomised to the long boost arm and has not previously received pertussis vaccine.**
 - Observation period post-vaccination for 20 minutes
- **Cohort 2.**
 - Vital signs pre-vaccination

- **Vaccination with COVID-19 vaccine if randomised to the short interval boost or no vaccine or dTaP/IPV if randomised to the long interval boost arm and has not previously received pertussis vaccine. If dTaP/IPV vaccination is requested, it should be given by 32 weeks' gestation and with an interval of at least 1 week before / after receipt of COVID-19 vaccine.**
- Observation period post-vaccination for 20 minutes
- **No vaccination for cohort 3 (28 0/7 – 34 0/7 gestational weeks at recruitment) and cohort 4 (COVID-19 vaccine received pre-pregnancy / first trimester (0 0/7 – 12 6/7 gestational weeks)).**

Study visit 4 (Maternal) Cohort 1 and 2 only

Day 56-84 following the first vaccination (or 28-42 days post-short interval boost dose) at the participating institution.

- SAE / AESI / MAAE check
- Concomitant medication check
- Diary card review if applicable
- Targeted physical examination if indicated
- Immunogenicity blood samples will be collected

- **Cohort 1.**
 - Vital signs pre-vaccination
 - **Vaccination with COVID-19 vaccine if randomised to the long interval boost or dTaP if randomised to the short interval boost arm and has not previously received the pertussis vaccine**
 - Observation period post-vaccination for 20 minutes
 - eDiary review

- **Cohort 2.**
 - Vital signs pre-vaccination
 - **Vaccination with COVID-19 vaccine if randomised to the long interval boost or no vaccine or dTaP/IPV if randomised to the short interval boost arm and has not previously received pertussis vaccine. If dTaP/IPV vaccination is requested, it should be given by 32 weeks' gestation and with an interval of at least 1 week before / after receipt of COVID-19 vaccine.**
 - Observation period post-vaccination for 20 minutes
 - eDiary review

- **No visit 4 for cohort 3 (28 0/7 – 34 0/7 gestational weeks at recruitment) and cohort 4 (COVID-19 vaccine received pre-pregnancy / first trimester (0 0/7 – 12 6/7 gestational weeks)).**

Study visit 5 (Maternal) Cohort 1 and 2 only

Day 84-112 following the first vaccination (or 28-42 days post-long boost dose) at the participating institution / participant home.

- SAE / AESI / MAAE check
- Concomitant medication check

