- eDiary review if applicable
- Targeted physical examination if indicated
- Immunogenicity blood samples will be collected
- **No visit 5 for cohort 3 (28 0/7 - 34 0/7 gestational weeks at recruitment) and cohort 4 (COVID-19 vaccine received pre-pregnancy / first trimester (0 0/7 – 12 6/7 gestational weeks)).**

Study visit 6 (Maternal) Cohort 1, 2 and 4 only

Day 112-140 following the first vaccination (or 56-84 days post second COVID-19 vaccine dose at the participating institution / participant home. This visit need only take place if the visit window starts before the due date.

- SAE / AESI / MAAE check
- Concomitant medication check
- eDiary review if applicable
- Targeted physical examination if indicated
- Immunogenicity blood samples will be collected
- **No visit 6 for cohort 3 (28 0/7 – 34 0/7 gestational weeks at recruitment).**

Study visit 7 (Delivery, maternal / infant)

Delivery at the participating institution.

- Targeted physical examination if indicated
- Immunogenicity maternal blood samples will be collected. These samples can be obtained by a member of the study team or a clinical member of staff. If blood sampling is not performed at delivery, women will be asked if a blood sample can be obtained from them within the first week following delivery and if a cord sample is not obtained parents will be asked if we can take a blood sample from the infant within the first week following delivery.
- Cord blood sample taken (at selected sites)

- Infant examination by clinical team

Study visit 8 (postnatal) only for participants in cohort 3 and / or in the breast milk sub-study

0 – 7 days post delivery where possible at the participating institution for those in the breast milk sub-study group and those due vaccination in cohort 3.

- SAE / AESI / MAAE check
- Concomitant medication check
- Targeted maternal physical examination for participants in cohort 3 only
- Colostrum sample collection (at selected sites). Participants who have agreed to take part in the breast milk sub-study will be asked if they still plan to breastfeed and if they are happy to provide a sample of colostrum. If women are still willing to take part in the study, they will be provided with information about colostrum sampling and containers and instructions for the collection of the sample.

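### The Visit 5 study window in both Cohort 1 and 2 schedule tables works out to the Visit 4 window and, if followed, would mistime the long arm's post-boost samples

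*Protocol*

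**What the plan says.** The Protocol times V5 for Cohorts 1 and 2 in three ways.

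- **Appendix 4 (Section 16.3), study-window row:** "Day 28-42 post V3", in both the visit schedule and the laboratory sampling schedule.
- **Appendix 4, timeline row, same column of both tables:** Day 84-112.
- **Section 7, Study visit 5:** "Day 84-112 following the first vaccination (or 28-42 days post-long boost dose) at the participating institution / participant home".

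The anchors are in Section 7. V3 is "Day 28-42 following the first vaccination at the participating institution". V4 is "Day 56-84 following the first vaccination (or 28-42 days post-short interval boost dose) at the participating institution". The long boost is given at V4; for Cohort 1 the text reads "Vaccination with COVID-19 vaccine if randomised to the long interval boost or dTaP if randomised to the short interval boost arm", and Cohort 2 follows the same rule.

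Footnote b of the visit schedule says participants are sampled for "Neutralising Antibody, ELISpot, Intracellular Cytokine Staining assays at V4 or V5 depending on whether they are on the short course or long course". V5 is therefore where the long arm's post-boost functional and cellular samples fall, and V4 is where the short arm's fall.

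For V6, Section 7 says "Day 112-140 following the first vaccination (or 56-84 days post second COVID-19 vaccine dose". In the tables the timeline row has Day 112-140, and the window row has 56-84 days after the second COVID-19 dose.

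**The concern.** V3 is the short arm's boost visit and precedes the long boost. A V5 window counted from V3 therefore cannot deliver a sample 28-42 days after a boost given at V4. The study-window row is what a site would naturally use to book visits and accept sample dates, and the same entry stands in the table that governs laboratory sampling.

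A sample drawn at the wrong time cannot be retaken. The mistiming relative to boost would fall on one randomised arm: long-arm samples would be taken before or soon after the boost and set beside short-arm samples taken 28-42 days after theirs. The rationale (Section 2) says longer intervals may improve antibody responses at some cost to cellular responses. The V4/V5 samples are those from which that contrast would be described at a like time after the boost.

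**Working it through.** **Inputs** (days after first dose; Section 7 and Appendix 4): V3 = 28-42. V4 = 56-84, with the long boost given there. V5 timeline = 84-112. V5 window = V3 + (28 to 42).

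**1. Does the window row reproduce the timeline row?**
- Earliest: 28 + 28 = Day 56. Latest: 42 + 42 = Day 84.
- The result, Day 56-84, is the V4 window. It meets the printed Day 84-112 only on Day 84. The timeline figure is not reproduced.

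**2. What does the window row imply for the long arm?**
- Days since boost = V5 - V4, at most 84 - 56 = 28.
- Whole-day combinations: 15 (V3) × 15 (offset) × 29 (V4) = 6,525.
- V5 falls before the boost in 3,150, on the same day in 225, and 1-28 days after it in the remaining 6,525 - 3,150 - 225 = 3,150.
- One combination gives a 28-42-day sample: V3 on Day 42, V4 on Day 56, V5 on Day 84, which is exactly 28 days.
- These are counts of possible dates, not probabilities.

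**3. What does anchoring to the long boost give?**
- 56 + 28 = Day 84 to 84 + 42 = Day 126. The start agrees with the timeline; the upper end exceeds Day 112.
- For a boost on day b, the days meeting both rules run from max(84, b + 28) to min(112, b + 42):

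| Long boost | V5 days meeting both rules |
|---|---|
| Day 56 | 84-98 |
| Day 70 | 98-112 |
| Day 84 | 112 only |

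Re-anchoring restores the sample, but the Day 112 limit still conflicts with the 28-42-day rule for later boosts.

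**4. V6: window of 56-84 days after dose 2 against Day 112-140.**
- Short arm: 28 + 56 = Day 84 to 42 + 84 = Day 126.
- Long arm: 56 + 56 = Day 112 to 84 + 84 = Day 168.
- The two rows overlap but differ. A short boost on Day 28 gives Day 84-112 (common day 112). A long boost on Day 84 gives Day 140-168 (common day 140).
- Keeping only Day 112-140 would put V6 at 112 - 42 = 70 to 140 - 28 = 112 days after a short boost, but 112 - 84 = 28 to 140 - 56 = 84 days after a long boost. The choice of anchor is a trade-off.

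**The case against.** The strongest reply is that the rest of the Protocol resolves the slip. The cell directly above the wrong one says Day 84-112 in both tables. Section 7 states the post-boost rule outright, and Section 7.7 and the endpoint lists treat Day 56-84 and Day 84-112 as separate sampling times. A V5 window that coincides with V4 is also something a site would be likely to query. This stands: the intention can be recovered, and the loss is conditional on sites following the window row.

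A reader might infer that the long arm loses its post-boost sample under the plan as written, in all 300 planned long-arm women (100 per arm × 3 vaccines, Section 10.1). The documents do not support that. The 300 is a ceiling that assumes every site follows the one wrong cell. Neutralising and cellular assays are planned only in subsets. In Cohort 2 a correctly timed V5 comes no earlier than 36 weeks (24 weeks + 84 days), so some women may deliver first.

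A reader might also infer a known bias against the long schedule. Samples taken before the boost would lack its effect, but the Protocol gives no antibody or cellular kinetics to show how samples up to 28 days after a boost compare with those at 28-42 days. Section 10 fixes no long-versus-short test at V5.

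On V6, Section 7 joins the two rules with an *or*, so it does not require both to be met. What remains is that the two rows of the tables disagree.

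**Conclusion.** The inconsistency is certain: the same wrong anchor stands in two operational tables and contradicts both the timeline row and Section 7. If the study-window row were followed, essentially all of the long arm's 28-42-day post-boost samples would be mistimed, with at most 28 days from boost to sample. This affects secondary immunogenicity comparisons. The primary endpoint (anti-spike IgG at delivery), its model and the sample size do not use V5 and are untouched.

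The conclusion rests on two assumptions: that sites would act on the study-window row, and that Section 7's 28-42-day rule governs the short arm's V4. The Day 56-84 window alone would allow 56 - 42 = 14 to 84 - 28 = 56 days after the short boost. The V5 upper limit and the V6 rules are smaller inconsistencies of the same kind.

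**What to change.** - In both Cohort 1 and 2 tables of Appendix 4, reconcile the V5 study window with the timeline row and Section 7, so that the long arm's V5 sample is anchored to the long boost at V4 and not to V3.
- Reconcile the Day 112 upper limit with the 28-42-day rule, which gives Day 84-126 for boosts on Day 56-84.
- Reconcile the V6 timeline row with its window row, and both with Section 7. Which anchor to keep is for the trial team, given the trade-off shown above.

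The core correction is one cell in each of two tables. If the V5 limit is moved, the Day 84-112 entries in the trial summary, Sections 3.5 to 3.7, Section 7 and Section 7.7 must follow, and any overlap with V6 from Day 112 must be addressed. No visit, sample or assay is added.
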